6. STUDY PROCEDURES

The study procedures to be conducted for each participant enrolled in the study are presented in tabular form in [Appendix 3](#) and described in the text that follows.

The investigator must document any deviation from the protocol procedures and notify Gilead or the CRO.

NOTE: Samples for laboratory safety assessments should be collected before dialysis on the day of dialysis for participants on intermittent RRT during the study.

6.1. Participant Enrollment and Treatment Assignment

Entry into screening does not guarantee enrollment into the study. In order to manage the total study enrollment, Gilead, at its sole discretion, may suspend screening and/or enrollment at any site or study-wide at any time.

6.2. Pretreatment Assessments

6.2.1. Screening Visit

Participants will be screened within 2 days before randomization to determine eligibility for participation in the study. The following will be performed and documented at screening:

- Obtain written informed consent (participant \geq 18 years of age) or assent from parent or legal guardian (participants $<$ 18 years of age, where locally and nationally approved)
- Determine eligibility requirements as specified in the inclusion and exclusion criteria
- Focused medical history will include date of first symptoms, overall symptoms, exposure source, demographics, baseline characteristics, concomitant medications, kidney or other transplant history, and allergies
- Complete physical examination, including vital signs (heart rate, temperature, blood pressure), actual body weight, and height
- Documentation of respiratory status:
 - Respiratory rate
 - Oxygenation: oxygen saturation (SpO₂), room air, low-flow O₂, high-flow O₂

CC

- Documentation of SARS-CoV-2 infection by PCR via 1 validated assay at a local laboratory, if not performed within the last 4 calendar days
- Document COVID-19 vaccine status (Note: It should be documented whether participant is fully or partially vaccinated, including any booster[s] received, if applicable.)
- Record the 8-point ordinal scale (see Section 6.9)
- Record any SAEs and all AEs related to protocol-mandated procedures occurring after signing of the informed consent (or assent) form
- IMV (yes/no; if yes, provide date when mechanical ventilation was started)
- RRT assessment
- If available, up to 3 SCr values prior to COVID-19 illness (eg, within the previous 6 months)
- Counsel participants of childbearing potential to use adequate birth control methods required during the trial to avoid pregnancy. See Appendix 4
- Laboratory evaluations: The following tests will be performed at screening. Results from within 48 hours prior to screening are acceptable; the entire panel of tests should be performed for all study participants if not done in the preceding 48 hours (see Section 6.5):
 - Chemistry, hematology, SCr, and coagulation
 - Urinalysis (participants who are oliguric are not required to provide a urine sample)
 - Pregnancy test (serum, for females of childbearing potential)

All other untoward medical occurrences observed during the screening period, including exacerbation or changes in medical history, are to be considered medical history. See Section 7, Adverse Events and Toxicity Management, for additional details.

6.2.2. Baseline/Day 1 Assessments

The following evaluations are to be completed at the Day 1 visit. The investigator must have confirmed eligibility (all inclusion/exclusion criteria must be met prior to randomization) before proceeding with Day 1 visit procedures.

Participants must complete the following assessments before being administered investigational drug:

- Vital signs (heart rate, temperature, blood pressure)
- Confirmed negative pregnancy test from screening visit (for women of childbearing age)

- Documentation of respiratory status:
 - Respiratory rate
 - Oxygenation: SpO₂, room air, low-flow O₂, high-flow O₂, and target fraction of inspired oxygen (FIO₂). The target FIO₂ value applies to all forms of O₂ nasal and mask delivery (nasal prongs, masks, CPAP/BIPAP) as well as mechanical ventilation.
- IMV (yes/no; if yes, provide date when mechanical ventilation was started)
- Assessment of need for RRT
- Record the 8-point ordinal scale twice (see Section 6.9)
- Review AEs and document concomitant medications
- Laboratory evaluations: Chemistry, hematology, coagulation, and SCr (see Section 6.5)
- Collection of nasopharyngeal swab sample for SARS-CoV-2 RT-qPCR testing **CCI**
[REDACTED] (see Section 6.8)

[REDACTED]

CCI [REDACTED]

[REDACTED]

6.4. Assessments (Days 2 Through 29)

The following evaluations are to be completed daily (unless otherwise noted in indicated sections and [Appendix 3](#)) from Day 2 through Day 29 or until discharge from inpatient hospitalization, whichever is earlier. If the participant is readmitted to the hospital prior to Day 29, evaluation for RRT, ordinal scale and AEs are to be completed daily through Day 29.

Participants must complete the following assessments before being administered investigational drug:

- Vital signs (heart rate, temperature, blood pressure)
- Documentation of respiratory status:
 - Respiratory rate
 - Oxygenation: SpO₂, room air, low-flow O₂, high-flow O₂, CPAP/BIPAP, mechanical ventilation, venovenous ECMO, venoarterial ECMO, and target FIO₂. The target FIO₂ value applies to all forms of O₂ nasal and mask delivery (nasal prongs, masks, CPAP/BIPAP) as well as mechanical ventilation

- IMV (yes/no; if yes, provide date when mechanical ventilation was started)
- Assessment of need for RRT
- Record the 8-point ordinal scale (see Section 6.9)
- Review AEs and document concomitant medications
- Laboratory evaluations: Chemistry, hematology, coagulation, and SCr (see Section 6.5)

█ [REDACTED]

█ [REDACTED]

- Collection of nasopharyngeal swab sample for SARS-CoV-2 RT-qPCR testing CCI [REDACTED]
[REDACTED] (see Section 6.8)

6.5. Additional Assessments

Laboratory testing during hospitalization will be performed according to SOC practice with results for chemistry, hematology, and any SARS-CoV-2 testing being reported to the sponsor.

In addition, even if not performed as SOC, the following will be completed at screening and on Days 1, 3, 5, 8, 12, 16, 20, 24, and 29 or until discharge, whichever is earlier:

- Laboratory evaluations: Chemistry, hematology, coagulation

In addition, even if not performed as SOC, the following will be completed at screening and on Days 1 through 29, or until discharge, whichever is earlier:

- Laboratory evaluations: SCr

CCI [REDACTED]

[REDACTED]

CCI [REDACTED]

CCI [REDACTED]

[REDACTED]

[REDACTED]

[REDACTED]

[REDACTED]

CCI [REDACTED]

[REDACTED]

[REDACTED] CCI [REDACTED] CCI [REDACTED]

[REDACTED]

CCI [REDACTED]

[REDACTED]

[REDACTED]

[REDACTED]

[REDACTED]

[REDACTED]

6.8. Virology Assessments

CCI

, CCI

Nasopharyngeal swab samples for SARS-CoV-2 RT-qPCR testing CCI will be collected from all participants on Days 1, 3, 5, 7, 14, 21, and 29 or until discharge, whichever is earlier

6.9. Ordinal Scale

The ordinal scale is an assessment of the clinical status of a given study day. Each day, the worst (ie, highest ordinal) score from the previous day will be recorded (ie, on Day 3, the highest ordinal score from Day 2 is obtained and recorded for Day 2). The ordinal scale needs to be completed twice on Day 1: prior to randomization (for baseline predose score) and the worst score on Day 1.

The scale is as follows:

- 8) Death
- 7) Hospitalized, on IMV or ECMO
- 6) Hospitalized, on noninvasive ventilation or high-flow oxygen devices
- 5) Hospitalized, supplemental oxygen
- 4) Hospitalized, not requiring supplemental oxygen – requiring ongoing medical care for COVID-19–specific medical care (other than per-protocol RDV administration)
- 3) Hospitalized, not requiring supplemental oxygen – no longer requires ongoing medical care (other than per-protocol RDV/saline as placebo administration)
- 2) Not hospitalized, limitation on activities and/or requiring home oxygen
- 1) Not hospitalized, no limitations on activities

6.10. Posttreatment Assessments

Upon discharge from inpatient hospitalization, the following assessments will be required at the Day 29 and Day 60 phone follow-up (see [Appendix 3](#)):

- Assessment of need for RRT
- Record the 8-point ordinal scale (see Section 6.9)
- Review AEs and document concomitant medications

- Mortality
- IMV (yes/no if yes, provide date when mechanical ventilation was started)
- Hospital readmission rate

6.11. Assessments for Early Discontinuation from Study

If a participant discontinues study dosing (eg, as a result of an AE), every attempt should be made to keep the participant in the study and continue to perform the required study-related follow-up and procedures (see Section 6.11.1, Criteria for Discontinuation of Study Treatment). If this is not possible or acceptable to the participant or investigator, the participant may be withdrawn from the study.

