5.1.3. Procedures for Breaking Treatment Codes

In the event of a medical emergency where breaking the blind is required to provide medical care to the participant, the investigator may obtain treatment assignment directly from the interactive voice/web response system for that participant. The designated Site Unblinder may record an emergency unblinding transaction to immediately receive the participant's randomized treatment assignment. Gilead recommends but does not require that the investigator contact the Gilead medical monitor before breaking the blind. Treatment assignment should remain blinded unless that knowledge is necessary to determine participant emergency medical care. The rationale for unblinding must be clearly explained in source documentation along with the date on which the treatment assignment was obtained. The investigator is requested to contact the Gilead medical monitor promptly in case of any treatment unblinding.

Blinding of study treatment is critical to the integrity of this clinical study. Therefore, if a participant's treatment assignment is disclosed to the investigator, the participant will have study treatment discontinued. All participants will be followed until study completion unless consent to do so is specifically withdrawn by the participant.

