8.7. Adjustments for Multiplicity

The overall two-sided Type I error rate of 0.05 for the primary and key α -controlled secondary end points will be controlled using the Lan-DeMets approach with O’Brien-Fleming type spending function accompanying a gatekeeping testing strategy (ie, the primary efficacy end point will be tested first and the key α -controlled secondary end point will be tested only if the primary efficacy end point is met). The α -spending and gatekeeping details are specified in Table 5.

Table 5. Gatekeeping and Boundaries for Efficacy Analysis

Efficacy Analysis	Primary End Point	Key α -controlled Secondary End Point (Will be Tested ONLY IF Primary End Point is Met)
Interim Analysis (50% of Participants Completed Day 29)	0.0031	0.0031
Primary Analysis (All Participants Completed Day 29)	0.0490 (will be tested ONLY IF the primary end point is NOT met at interim)	0.0490

Note: P-values are based on two-sided stratified log-rank test.

CCI [REDACTED]

7 [REDACTED]

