8.9. Sample Size

A total of approximately 1116 participants will be randomized in a 2:1 ratio to 2 groups (744 in the RDV group and 372 in the saline as placebo group). This sample size achieves approximately 85% power to detect a hazard ratio of 0.70 at a two-sided alpha level of 0.05. In the sample size calculation, it is assumed that the event rate in the saline as placebo group is 35%. The hazard ratio and event rate in the saline as placebo group are based on the most conservative estimates of the primary end point (composite of all-cause mortality or IMV) and key α -controlled secondary end point (all-cause mortality) through Day 29 among a subset of participants with eGFR < 60 mL/min in the Division of Microbiology and Infectious Diseases Protocol 20-0006 Adaptive COVID-19 Treatment Trial (ACTT)-1 (hazard ratio of 0.67 and placebo rate of 33%).

The sample size calculation was done using software EAST (Version 6.5, module for log-rank test given accrual duration [120 days] and study duration [149 days] and 1 interim analysis using the Lan-DeMets approach with O’Brien-Fleming type spending function).

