6.1.3. Primary Analysis of the Primary Efficacy Endpoint

The primary endpoint will be analyzed using a stratified log-rank test stratified by the randomization strata. P value and the proportion of all-cause mortality or IMV at Day 29 from Kaplan-Meier estimate will be provided.

The hazard ratio and 95% confidence interval (CI) will be estimated using a Cox model with stratification factors as covariates.

Participants with missing outcomes for the primary endpoint due to premature discontinuation of the study on or prior to Day 29 will be censored at the last study day.

Additionally, the difference in proportions of all-cause mortality or IMV at Day 29 between treatment groups and the 95% CI for the difference will be provided based on the stratum-adjusted Mantel-Haenszel (MH) proportion as described in {Koch 1989} in [Appendix 2](#).

The FAS will be the primary analysis set for efficacy endpoint evaluation.

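### Protocol 6.11 lets the investigator end all study follow-up after a drug stop without withdrawn consent, which is inconsistent with 5.1.3 and 3.5 and can lose primary-endpoint outcomes that are easy to collect

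*Protocol*

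**What the plan says.** Four parts of the protocol and two of the SAP bear on this.

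- **Protocol 6.11** covers a participant who discontinues dosing, for example because of an adverse event. It asks for every attempt at retention with the required follow-up. It then says: "If this is not possible or acceptable to the participant or investigator, the participant may be withdrawn from the study".
- **Protocol 5.1.3**, on breaking treatment codes, requires study treatment to stop when the assignment is disclosed to the investigator. It continues: "All participants will be followed until study completion unless consent to do so is specifically withdrawn by the participant".
- **Protocol 3.5** lists reasons for holding or stopping dosing. It then requests that all participants continue assessments through Day 29 and take the Day 60 call. It gives the investigator no opt-out.
- **Protocol 8.5.1** censors participants whose primary outcome is missing because they left the study early, at the date of last contact.
- **SAP 6.1.3** says that missing outcomes "due to premature discontinuation of the study on or prior to Day 29 will be censored at the last study day".
- **SAP 6.1.4** offers one sensitivity analysis for missing outcomes. It is optional and counts early leavers as having had no event.

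**The concern.** Stopping a drug and leaving a study are different events, and 6.11 lets the first lead to the second on the investigator's judgement alone. The endpoint is death or invasive mechanical ventilation (IMV). Both can be established at Day 29 without any of the daily study procedures, so losing them is avoidable.

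The reasons for stopping drug in 6.11.1 include suspected drug-related serious or Grade 3 or higher events, transaminase elevation, toxicity and intercurrent illness. Some of these plausibly track the risk of death or IMV, and some could differ between arms. If both hold for the people withdrawn, the censoring is informative and the primary hazard ratio is biased. If neither holds, the cost is lost events and lost power. The optional analysis in SAP 6.1.4 would not detect informative censoring, because it assumes that every early leaver stayed event-free.

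**Working it through.** **1. Do the sections conflict?** Take a participant whose assignment is disclosed to the investigator on Day 3. Under 5.1.3 drug stops, and follow-up continues unless that participant withdraws consent. The same person has discontinued dosing, so 6.11 also applies and allows study withdrawal if the investigator finds continuation unacceptable. The two rules give different answers for the same person. For drug stops without unblinding, the 5.1.3 sentence still refers to all participants, and 3.5 asks for continued assessment. The inconsistency remains there, though less sharply.

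**2. How much follow-up is at stake?** Withdrawal on Day 3 loses 29 − 3 = 26 days. Withdrawal on Day 5 loses 29 − 5 = 24 days.

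**3. Reproduce the plan's own figure.** Protocol 8.9: "This sample size achieves approximately 85% power to detect a hazard ratio of 0.70 at a two-sided alpha level of 0.05". Inputs from that section: 744 remdesivir (RDV), 372 placebo, placebo event rate 35%.

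- RDV rate = 1 − 0.65^0.70 = 26.0%
- Expected events = 372 × 0.35 + 744 × 0.260 = 130 + 194 = 324
- Schoenfeld power = Φ(|ln 0.70| × √(324 × 2/3 × 1/3) − z) = 85.7% at alpha 0.05, and 85.5% at the 0.0490 final level in protocol Table 5

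The stated power is reproduced and is not in dispute. The sample-size text mentions no allowance for withdrawal.

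**4. Illustrate the bias.** Every withdrawal input here is an assumption. Let w be the share of an arm withdrawn early and r the true Day 29 risk of those withdrawn. All their events are taken as lost. True risk is 35% in both arms, so the true hazard ratio is 1.00.

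- Observed risk = (0.35 − w·r)/(1 − w)
- Apparent HR = ln(1 − observed RDV risk)/ln(1 − observed placebo risk)
- Events lost = (744·w_RDV + 372·w_placebo)·r

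| w RDV / placebo | r | Observed risk RDV / placebo | Apparent HR | Events lost |
|---|---|---|---|---|
| 4% / 1% | 50% | 34.4% / 34.8% | 0.98 | 17 |
| 4% / 1% | 70% | 33.5% / 34.6% | 0.96 | 23 |
| 6% / 2% | 50% | 34.0% / 34.7% | 0.98 | 26 |
| 6% / 2% | 70% | 32.8% / 34.3% | 0.95 | 36 |
| either split | 35% | 35.0% / 35.0% | 1.00 | 12–18 |

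Under the null, swapping the arms gives the reciprocals, from 1/0.983 = 1.02 to 1/0.946 = 1.06. The direction therefore depends on which arm loses more high-risk participants.

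**5. Check with a second model.** This uses a Cox hazard ratio with constant hazards over 29 days. A share of each arm is censored at Day 4, with 2 or 3 times the hazard of the rest of its arm. True HR is 1.00.

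- 5% / 2% withdrawn: 0.98 or 0.97
- 10% / 5% withdrawn: 0.97 or 0.95
- 10% / 2% withdrawn: 0.95 or 0.92
- 5% / 5% withdrawn, or average-risk withdrawal: 1.00

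**6. Scale.** At 324 events the standard error of the log hazard ratio is 1/√(324 × 2/9) = 0.118. The shifts in step 4 are 0.14 to 0.48 standard errors. Loss unrelated to risk costs only events: 5% loss leaves about 308 events and 83.7% power, and 10% leaves about 291 and 81.6% (alpha 0.049). SAP 2.4 says enrolment stopped before half the planned number, so the event counts in the table would be at most half as large in the trial as run.

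**The case against.** The strongest defence is that 6.11 already makes retention the default. The quoted sentence comes after the instruction to make every attempt, it says only that a participant may be withdrawn, and 3.5 points the same way. A reader might infer that drug stops as a rule become censored outcomes. The text does not support that; it opens a route.

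A reader might also infer a flat contradiction with 5.1.3 for every participant. That sentence closes the code-breaking section and bites hardest for unblinded participants. For others, a general aim sits beside an exception.

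Nor are all deaths necessarily lost. Protocol 7.3.3 asks for serious events and deaths within 30 days of the last dose to be reported. Even after a single dose on Day 1 that window reaches Day 31. SAP 3.8.1 anticipates knowing of some deaths after early study exit: it excludes them from the Last Study Date but does not say whether they count as endpoint events. These provisions reduce the loss of deaths. They do little for IMV, which is not itself listed as a reportable event in 7.3.3, and investigators are not obliged to seek events actively once follow-up has ended.

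Finally, a reader might infer a bias that favours RDV. That needs higher risk and an excess of withdrawals in the RDV arm among the same people. Stops for drug toxicity may differ by arm without carrying a higher risk of death or IMV. Stops for deterioration carry higher risk but, if RDV works, would be more common on placebo. Discharge is also a stopping reason in 3.5, and such participants are presumably at lower risk. This objection stands: the direction is unknown.

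What survives is that a willing participant's outcome follow-up can be ended by someone else, against the standard stated elsewhere in the protocol and for no purpose that the protocol states.

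**Conclusion.** The inconsistency between 6.11 and both 5.1.3 and 3.5 is in the text, and the route from drug stop to censored primary outcome follows from protocol 8.5.1 and SAP 6.1.3. The loss is avoidable, because protocol 6.10 already collects mortality and dated IMV by phone at Day 29 after discharge.

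The size cannot be derived from the documents. The 0.95–0.98 range under a true HR of 1.00 rests on assumed withdrawal of 4–6% on RDV against 1–2% on placebo, on 50–70% risk in those withdrawn, and on complete loss of their events. It also attributes all of those withdrawals to this clause, whereas the clause adds only people willing to stay whom the investigator removes. That makes the range generous. Equal withdrawal gives no bias under the null, and average-risk withdrawal gives none.

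This is a cheap improvement worth making, not evidence that the primary result is biased.

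**What to change.** Reconcile 6.11 with 5.1.3 and 3.5:

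- Remove the investigator's option to end outcome follow-up after a drug stop.
- State that stopping study drug is not a reason to leave the study.
- State that vital status and IMV (yes/no, with date) are followed to Day 29, through the existing phone contact or by chart review, unless the participant or legal representative withdraws consent to follow-up. The representative must be named because inclusion criterion 6 admits participants through representatives and under emergency provisions.
- Let the investigator omit burdensome study procedures while outcome follow-up continues.

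The criteria for stopping drug are not touched.

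Because enrolment has closed, the practical use now is to seek Day 29 status for anyone already withdrawn, where consent allows. A sensitivity analysis that allows a higher event risk after withdrawal could be added to SAP 6.1.4 before unblinding.

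The cost is a short protocol wording change and a few more calls or chart checks.

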6.11.1. Criteria for Discontinuation of Study Treatment

Study medication may be discontinued in the following instances:

- Any SAE or \geq Grade 3 AE suspected to be related to RDV
- Any elevations in ALT or AST $> 5 \times$ ULN
- Intercurrent illness that would, in the judgment of the investigator, affect assessments of clinical status to a significant degree. Following resolution of intercurrent illness, the participant may resume study dosing at the discretion of the investigator
- Unacceptable toxicity or toxicity that, in the judgment of the investigator, compromises the ability to continue study-specific procedures or is considered to not be in the participant's best interest
- Participant request to discontinue for any reason
- Participant noncompliance
- Pregnancy during the study (refer to [Appendix 4](#))
- Discontinuation of the study at the request of Gilead, a regulatory agency or an institutional review board (IRB) or independent ethics committee (IEC)

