3.5. Discontinuation Criteria

Investigational drug dosing in an individual participant will be placed on hold and may be discontinued, following a review of all available clinical data by the medical monitor and discussion with the investigator, if any of the following occurs:

- Any SAE or \geq Grade 3 AE suspected to be related to RDV

Any elevations in alanine aminotransferase (ALT) or aspartate aminotransferase (AST) $> 5 \times$ the upper limit of normal (ULN), confirmed by immediate repeat testing

- Discharge from the hospital/institution
- Intercurrent illness that would, in the judgment of the investigator, affect assessments of clinical status to a significant degree. Following resolution of intercurrent illness, the participant may resume study dosing at the discretion of the investigator

- Unacceptable toxicity, or toxicity that, in the judgment of the investigator, compromises the ability to continue study-specific procedures or is considered to not be in the participant's best interest
- Participant request to discontinue for any reason

All participants will be requested to continue assessments during study hospitalization and any subsequent re-hospitalization to the same institution during Days 1 through 29 and attend the Day 60 phone follow-up (whether hospitalized or as an outpatient).

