7.7. Toxicity Management

Infusion-related reactions have been observed during and following administration of RDV. Signs and symptoms may include hypotension, hypertension, tachycardia, bradycardia, hypoxia, fever, dyspnea, wheezing, angioedema, rash, nausea, diaphoresis, and shivering. Slower infusion rates, with a maximum infusion time of up to 120 minutes, can be considered to potentially prevent these signs and symptoms. If signs and symptoms of a severe infusion-related reaction occur, immediately discontinue administration of RDV and initiate appropriate treatment. Remdesivir infusions will be administered to participants at the site under close supervision. Healthcare professionals administering RDV infusions must have the appropriate medication available for immediate use in case of hypersensitivity or infusion-related reactions. The participant should be treated according to the SOC for management of hypersensitivity reaction or infusion-related reactions. Participants should be monitored for at least 2 hours after the RDV infusion is completed.

All clinical events and clinically significant laboratory toxicities will be managed according to uniform guidelines detailed in [Appendix 6](#), and as outlined below.

Grade 3 or 4 clinically significant laboratory abnormalities that were not present at baseline should be confirmed by repeat testing as soon as possible, and preferably within 3 calendar days after receipt of the original test results.

The Gilead medical monitor should be consulted prior to investigational drug discontinuation when medically feasible.

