7.7.2. Grade 3 Laboratory Abnormalities

For a Grade 3 clinically nonsignificant laboratory abnormality (eg, clinically insignificant Grade 3 cholesterol, triglyceride abnormalities, or creatine kinase (CK) elevations) that were not present at baseline, the investigational drug may be continued if the event is considered to be unrelated to the investigational drug.

For a Grade 3 clinically significant laboratory abnormality confirmed by repeat testing (as soon as possible, and preferably within 3 calendar days after receipt of the original test results), that was not present at baseline and considered to be related to the investigational drug, the investigational drug should be permanently discontinued and the participant managed according to local practice. The Gilead medical monitor should be consulted prior to investigational drug discontinuation when medically feasible.

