7.7.3. Grade 4 Laboratory Abnormalities

For a Grade 4 clinically significant laboratory abnormality by repeat testing (as soon as possible, and preferably within 3 calendar days after receipt of the original test results), that was not present at baseline and considered to be related to the investigational drug, the investigational drug should be permanently discontinued and the participant managed according to local practice. The Gilead medical monitor should be consulted prior to investigational drug discontinuation when medically feasible. The participant should be followed as clinically indicated until the laboratory abnormality returns to baseline or is otherwise explained, whichever occurs first. A clinically significant Grade 4 laboratory abnormality that is not confirmed by repeat testing should be managed according to the algorithm for the new toxicity grade.

Investigational drug may be continued without dose interruption for a clinically nonsignificant Grade 4 laboratory abnormality (eg, Grade 4 CK elevation after strenuous exercise, triglyceride elevation that is nonfasting or that can be medically managed) or a clinical event considered unrelated to the investigational drug.

Treatment-emergent toxicities will be noted by the investigator and brought to the attention of the Gilead medical monitor, and the appropriate course of action will be discussed and decided. Whether or not considered treatment related, all participants experiencing AEs must be monitored periodically until symptoms subside, any abnormal laboratory values have resolved or returned to baseline levels or they are considered irreversible, or until there is a satisfactory explanation for the changes observed.

Any questions regarding toxicity management should be directed to the Gilead medical monitor.

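### Protocol Sections 3.5 and 6.11.1 attach different instructions to the same two safety triggers, and Sections 7.7.2 and 7.7.3 are firmer for an overlapping laboratory case

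*Protocol*

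**What the plan says.** - **Section 3.5** opens with "Investigational drug dosing in an individual participant will be placed on hold and may be discontinued, following a review of all available clinical data". That review falls to the medical monitor, who also discusses the case with the investigator. Its triggers include a related SAE or Grade 3 or higher AE, and ALT or AST above 5 × ULN "confirmed by immediate repeat testing".
- **Section 6.11.1** repeats both triggers under the lead-in "Study medication may be discontinued in the following instances". The hepatic line begins "Any elevations in ALT or AST" and has no repeat-test condition. Neither a hold nor a monitor review is mentioned.
- **Section 7.7** asks for new, clinically significant Grade 3 or 4 laboratory abnormalities to be repeated as soon as possible, and "preferably within 3 calendar days after receipt of the original test results".
- **Section 7.7.2** says that for a confirmed, related Grade 3 abnormality of this kind "the investigational drug should be permanently discontinued and the participant managed according to local practice".
- **Section 7.7.3** has the same directive for Grade 4: "considered to be related to the investigational drug, the investigational drug should be permanently discontinued".

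Sections 7.7 to 7.7.3 also ask that the medical monitor be consulted before drug is stopped, when feasible. Section 7.7 points to Appendix 6 for uniform guidelines. None of Sections 3.5, 6.11.1 and 7.7 refers to the others or says which prevails.

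**The concern.** An investigator who consults Section 6.11.1, the section titled as the stopping criteria, would not learn that Section 3.5 makes a hold mandatory or that an ALT/AST elevation is to be repeated at once. Two sites could then handle the same hepatic event differently while each follows the protocol as it reads it. That is first a matter of participant safety: the population has severely reduced kidney function, and the first DMC review was directed at renal and hepatic toxicity.

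It also touches the data. AEs leading to drug discontinuation are a listed secondary end point (Protocol Sections 3.1 and 8.1.3), are tabulated under SAP Section 7.1.6, and form one limb of the treatment-emergent definition in SAP Section 7.1.5.1. Under Protocol Section 7.6, a laboratory abnormality that leads to interruption or discontinuation must be recorded as an AE. A site that holds drug under Section 3.5 may therefore record an event that a site continuing under Section 6.11.1 need not.

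**Working it through.** **Step 1: the instructions side by side**

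| | Section 3.5 | Section 6.11.1 | Sections 7.7.2 and 7.7.3 |
|---|---|---|---|
| Event | Related SAE or Grade ≥ 3 AE; ALT/AST > 5 × ULN | The same two | Laboratory abnormality, Grade 3 or 4, clinically significant, related, new since baseline, confirmed |
| Hold | Required | Not stated | Not stated |
| Medical monitor | Review precedes discontinuation | Not stated | Consulted before stopping, when feasible |
| Repeat test | Immediate, for ALT/AST | Not stated | As soon as possible, preferably within 3 calendar days |
| Discontinuation | Optional | Optional | Permanent (directive) |

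Sections 3.5 and 6.11.1 agree that discontinuation is optional. They differ on hold, review and ALT/AST confirmation. Sections 7.7.2 and 7.7.3 differ from both on whether stopping is optional, but only for an event that meets both descriptions, such as a related, clinically significant Grade 3 or 4 laboratory abnormality recorded as an AE.

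**Step 2: the confirmation window against the dosing period**

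Inputs:
- Dosing is once daily on Days 1 to 5 at most (Sections 3.4 and 5.3).
- Mandated chemistry, hematology and coagulation in that period fall on Days 1, 3 and 5 (Section 6.5).
- The Day 1 sample is predose (Section 6.2.2), so Day 3 is the first scheduled on-treatment panel.
- The documents give no laboratory turnaround, so 0 and 1 day are assumed.

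Formula: end of preferred window = sample day + turnaround + 3. The doses given by then assume that no hold is applied. Where two counts appear, the lower applies if the repeat result precedes that day's dose.

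| Sample | Turnaround 0 days | Turnaround 1 day |
|---|---|---|
| Day 1, postdose (unscheduled) | Day 4; 3 or 4 doses | Day 5; 4 or 5 doses |
| Day 2 (daily SCr or routine-care tests) | Day 5; 4 or 5 doses | Day 6; 5 doses |
| Day 3 (scheduled) | 3 + 0 + 3 = Day 6; 5 doses | Day 7; 5 doses |
| Day 4 (daily SCr or routine-care tests) | Day 7; 5 doses | Day 8; 5 doses |
| Day 5 (scheduled) | Day 8; 5 doses | Day 9; 5 doses |

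For both scheduled on-treatment panels the preferred window ends after the last possible dose.

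**Step 3: doses affected**

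Section 6.4 places the daily assessments before that day's dose. For a Day 3 result received the same day, the doses that a hold could affect are Days 3, 4 and 5 (three) if the result arrives before dosing, or Days 4 and 5 (5 − 3 = two) if it arrives after. For a same-day Day 5 result the number is one or none.

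**The case against.** The best defence is that the sections can be read in sequence: hold and review under Section 3.5, then a permanent stop if the narrower conditions of Sections 7.7.2 and 7.7.3 are met. Silence in Section 6.11.1 about a hold does not cancel a hold required elsewhere, and a site can comply with both. Medical monitor involvement, in Section 3.5 and Sections 7.7 to 7.7.3, gives some consistency across sites. Appendix 6 may already supply an algorithm; only its heading is visible in the text available here, so nothing can be held against it.

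Much of this stands. It limits the three-way difference to the overlapping laboratory case. It does not remove the difference between Sections 3.5 and 6.11.1, because a reader of the second is not directed to the first.

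Three stronger readings are tempting and are not supported:
- **That all three sections conflict on every trigger.** Section 7.7 is narrower. The ALT/AST trigger in the other two sections carries no relatedness condition, and their AE trigger also covers clinical events.
- **That the protocol lets the whole course be given before its stopping rule applies.** The 3 days are a preference following as soon as possible, and Section 3.5 separately asks for an immediate ALT/AST repeat. All five doses can precede confirmation only if the Section 3.5 hold is not applied.
- **That the discontinuation end point is biased.** The end point counts what happened. In a blinded randomized trial the ambiguity reaches both arms, and nothing in the documents shows a difference between them.

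**Conclusion.** The inconsistency is real and should be corrected. For the same two triggers, Section 3.5 says "Investigational drug dosing in an individual participant will be placed on hold and may be discontinued" while Section 6.11.1 leaves out the hold, the review and the ALT/AST confirmation. For the overlapping laboratory case, stopping is optional in two sections and a directive in two others.

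The practical size is bounded by the short course: at most three doses for a Day 3 result received the same day, and only where a site follows Section 7.7 or 6.11.1 without the Section 3.5 hold. That count assumes same-day receipt and a repeat as late as the preferred limit; a faster repeat reduces it. The documents do not say how many participants met a trigger, so the effect on AE or discontinuation counts cannot be estimated. The likely statistical consequence is site-to-site variation in recording, not a directional effect. The conclusion is also subject to what Appendix 6 contains.

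**What to change.** Reconcile Sections 3.5, 6.11.1 and 7.7 to 7.7.3, after checking them against Appendix 6, into one cross-referenced rule per trigger. Each rule should state whether a hold applies, whether and how quickly a repeat test is needed, and when stopping is permanent. That content is for the sponsor's clinical team; this review takes no view on which existing instruction is right. The cost is protocol wording.

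SAP Section 2.4 records that enrollment was stopped early, and the course lasts at most 5 days, so dosing is likely complete and rewording may no longer alter conduct. In that case the CSR should state which rule sites followed. AEs leading to discontinuation should be counted as they occurred, not reclassified against a rule settled afterwards, which could discard real discontinuations. The cost is a short statement in the CSR and no new data collection, provided site practice can be established from existing records.
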